8.5 Procedures

Previous procedures and concomitant procedures will be summarised for the Safety Set through frequency distributions and percentages by MedDRA SOC and PT.

The procedures will be classified according to the following rules:

- previous procedures: procedure start date < date of first study drug inhalation and end procedure date \leq date of first study drug inhalation;

- concomitant procedures: date of first study drug inhalation \leq procedure end date;
- post-study procedures: procedure start date \geq date of discharge.

8.6 Compliance

Treatment Compliance

In general, treatment compliance will be evaluated on the basis of the information recorded in the eCRF.

Number of correct and incorrect inhalations, number of interruptions during the infusion will be summarized using descriptive statistics on Safety population.

In addition, all variables related to the inhalation and to the IV infusion will be listed.

9 Pharmacokinetics Analyses

9.1 Pharmacokinetic Analysis

The concentration ratios of whole blood [^{14}C]-total and [^{14}C]-CHF6001 radioactivity to plasma [^{14}C]-total and [^{14}C]-CHF6001 radioactivity, individual and cumulative mass balance of [^{14}C]-total radioactivity (amount (Ae_u , cumulative Ae_u , Ae_f and cumulative Ae_u) and percentage of dose (fe_u , Fe_u , fe_f and Fe_f) recovered as [^{14}C]-total radioactivity in urine, feces and total excreta) will be calculated by radioanalysis laboratory (██████████).

In addition, metabolites in plasma accounting for $\geq 10\%$ of total radioactivity recovered in this matrix, structural characterization may be performed, where possible. For metabolites in urine and feces (total excreta) accounting for $\geq 10\%$ of total administered radioactivity, structural characterization may be performed, where possible.

If available, fraction of the relevant metabolites in plasma ($\text{Fr}_{\text{plasma}}$), fraction of the relevant metabolites recovered in urine and feces (Fr_{urine} , Fr_{feces} , $\text{Fr}_{\text{urine+feces}}$) will be reported in a separate report together with structural characterization performed by radioanalysis laboratory (██████████).

Urine and Feces [^{14}C]-CHF6001 and [^{14}C]-total radioactivity

Parameter	Units ^a	Definition
Ae_u	mg	amount excreted in urine (expressed in weight) over sampling interval
Cumulative Ae_u	mg	cumulative amount excreted in urine, calculated as the sum of the amount excreted in urine for each collection period
fe_u	%	percent of the dose excreted in urine over a sampling interval
Fe_u	%	cumulative percent of dose excreted in urine, calculated as the sum of the percent of dose excreted in urine for each collection period
Ae_f	mg	amount excreted in the feces over sampling interval
Cumulative Ae_f	mg	cumulative amount excreted in feces, calculated as the sum of the amount excreted in feces for each collection period
fe_f	%	percent of the dose excreted in feces over a sampling interval

Fe _f	%	cumulative percent of dose excreted in feces, calculated as the sum of the percent of dose excreted in feces for each collection period
CL _R	L/h	renal plasma clearance (urine [¹⁴ C]-CHF6001 only)
CL _{R_blood}	L/h	renal blood clearance where CL _{R_blood} = CL _R /R _{b/p} (urine [¹⁴ C]-CHF6001 only)
E _{h blood}		hepatic extraction calculated from intravenous systemic and renal blood clearance (CL _{blood} = CL/R _{b/p}) and CL _{R_blood} = CL _R /R _{b/p} , respectively and human hepatic blood flow (Q _H ; assumed to be 87 l/h). E _{h blood} = (CL _{blood} - CL _{R_blood})/ Q _H
Cumulative Ae _{u+f}	mg	cumulative amount excreted in urine and feces, calculated as Cumulative Ae _u + Cumulative Ae _f
Fe _{tot}	%	cumulative amount excreted in urine and feces, calculated as Fe _u + Fe _f
Fe _{met}		metabolized fraction calculated as Fe _{met} = [cumulative Ae _{u+f} (¹⁴ C-total) - cumulative Ae _{u+f} (¹⁴ C]-CHF6001)]/ cumulative Ae _{u+f} (¹⁴ C-total)

^a Units are based on concentration units (provided by the bioanalytical lab or preferred units for presentation of PK parameters) and dose units used in the study.

The following PK parameters will be determined by [REDACTED] where possible from the plasma concentrations of CHF6001 following inhaled administration using noncompartmental methods in validated software program Phoenix WinNonlin (Phoenix WNL, Certara, Version 8.1 or higher):

Parameter	Units ^a	Definition
AUC _(0-t) _inh	h*xg/mL	area under the concentration-time curve from 0 to the last quantifiable concentration (t _{last}) ^b
AUC _(0-∞) _inh	h*xg/mL	area under the concentration-time curve extrapolated to infinity ^c
%AUC _{extrap}	%	percentage of AUC due to extrapolation from the last quantifiable concentration to infinity
C _{max_inh}	xg/mL	the value of the maximum observed concentration
t _{max_inh}	h	the time of the maximum observed concentration
t _{last_inh}	h	the time of the last quantifiable concentration
t _{1/2_inh}	h	terminal half-life
F _{inh}		inhaled absolute bioavailability based on AUC _(0-∞)

^a Units are based on concentration units (provided by the bioanalytical lab or preferred units for presentation of PK parameters) and dose units used in the study.

^b Area under the concentration-time curve will be calculated using the linear trapezoidal rule with linear interpolation

^c Based on the last observed quantifiable concentration

The following PK parameters will be determined where possible from the plasma, whole blood, urine and feces [¹⁴C]-CHF6001 concentrations, plasma whole blood, urine and feces [¹⁴C]-total concentrations following intravenous (IV) infusion administration of [¹⁴C]-CHF6001 in each subject using noncompartmental methods in validated software program Phoenix WNL (Certara, Version 8.1 or higher):

Plasma [¹⁴C]-CHF6001 and [¹⁴C]-total radioactivity

Parameter	Units ^a	Definition
[¹⁴ C]- CHF6001 and [¹⁴ C]- Total	AUC _(0-t) _iv	h*xg/mL area under the concentration-time curve from 0 to the last quantifiable concentration (t _{last}) ^b
[¹⁴ C]- CHF6001 and [¹⁴ C]- Total	AUC _(0-∞) _iv	h*xg/mL area under the concentration-time curve extrapolated to infinity ^c
[¹⁴ C]- CHF6001 and [¹⁴ C]- Total	%AUC _{extrap}	% percentage of AUC due to extrapolation from the last quantifiable concentration to infinity
[¹⁴ C]- CHF6001 and [¹⁴ C]- Total	C _{max_iv}	xg/mL the value of the maximum observed concentration
[¹⁴ C]- CHF6001 and [¹⁴ C]- Total	t _{max_iv}	h the time of the maximum observed concentration
	t _{last_iv}	h the time of the last quantifiable concentration
[¹⁴ C]- CHF6001 and [¹⁴ C]-Total	t _{1/2_iv}	h terminal half-life
[¹⁴ C]- CHF6001	CL	L/h total body plasma clearance (plasma [¹⁴ C]-CHF6001)
[¹⁴ C]- CHF6001	V _z	L volume of distribution during the terminal phase (plasma [¹⁴ C]-CHF6001)
[¹⁴ C]- CHF6001	V _{dss}	L volume of distribution at steady state (plasma [¹⁴ C]-CHF6001)
Plasma concentration of [¹⁴ C]-CHF6001/Total Radioactivity Ratio	NA	ratio of plasma concentration of [¹⁴ C]-CHF6001 to plasma concentration of [¹⁴ C]-total
AUC _(0-∞) Plasma [¹⁴ C]-CHF6001/Total Radioactivity Ratio	NA	AUC _(0-∞) of plasma [¹⁴ C]-CHF6001 relative to AUC _(0-∞) of plasma [¹⁴ C]-total radioactivity
C _{max} Plasma [¹⁴ C]-CHF6001/Total Radioactivity Ratio	NA	C _{max_iv} of plasma [¹⁴ C]-CHF6001 relative to C _{max_iv} of plasma [¹⁴ C]-total radioactivity

^a Units are based on concentration units (provided by the bioanalytical lab or preferred units for presentation of PK parameters) and dose units used in the study. For total radioactivity, C_{max} and AUC units will be presented as mass equivalents (ng Eq/g and h*ng Eq/g, respectively).

^b Area under the concentration-time curve will be calculated using the linear trapezoidal rule with linear interpolation

^c Based on the last observed quantifiable concentration

Blood [¹⁴C]-CHF6001 and [¹⁴C]-total radioactivity

Parameter	Units	Definition
[¹⁴ C]-CHF6001	R _{b/p}	NA whole blood to plasma ratio is to be determined on the [¹⁴ C]-CHF6001 whole blood and plasma concentration (C _b and C _p) 20 minutes after the start of infusion, calculated as R _{b/p} = C _b /C _p
[¹⁴ C]-total	R _{bt/pt}	NA whole blood to plasma ratio is to be determined on the total-[¹⁴ C] whole blood and plasma concentration (C _{bt} and C _{pt}) 20 minutes after the start of infusion, calculated as R _{bt/pt} = C _{bt} /C _{pt}

Additional PK parameters may be determined where appropriate.

Concentration ratios of plasma [¹⁴C]-CHF6001 to plasma [¹⁴C]-total radioactivity will be listed by time point and summarized.

Pharmacokinetic analysis will be carried out using actual dose administered (mg) and actual blood sampling times post-dose. If an actual time is missing, the sample concentration result will be treated as missing unless there is scientific justification to include the result using the nominal time.

The parameters C_{max_inh}, C_{max_iv}, t_{last_inh}, t_{last_iv}, t_{max_inh} and t_{max_iv} will be obtained directly from the concentration-time profiles. If C_{max} occurs at more than 1 timepoint, t_{max} will be assigned to the first occurrence of C_{max}.

Inhaled absolute bioavailability (F_{inh}) based on AUC_(0-∞) will be calculated as follows:

$$F_{inh} = (AUC_{(0-∞)_inh} \times Dose_{iv}) / (AUC_{(0-∞)_iv} \times Dose_{inh}).$$

The parameter AUC_(0-t) or other common partial area may be used to determine F_{inh}, metabolite and total radioactivity ratios if AUC_(0-∞) cannot be reliably calculated for the majority of subjects.

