9.5 Calculation of [¹⁴C]-CHF6001 and [¹⁴C]-total radioactivity Feces Parameters

The amount of the dose administered recovered (Aef) in feces as [¹⁴C]-CHF6001 for each faecal collection interval (t_1-t_2) will be calculated as concentration in faecal collected sample and faecal collected sample weight. A total cumulative $Aef_{0-x\ h}$ will be calculated by summing across collection intervals over the 0-x h interval, where x = end of the last collection time interval.

The percentage of the dose administered recovered in feces over the time interval t_1 to t_2 (fe_{f,t_1-t_2}) as [¹⁴C]-CHF6001 will be calculated for each faecal collection interval as follows:

$$fe_{f,t_1-t_2} = (Aef_{t_1-t_2} / Dose_{IV}) \times 100$$

Cumulative fe_f (Fe_f) will be calculated by summing the fe_{f,t_1-t_2} values across collection intervals in the same manner as cumulative Aef.

The fraction of the relevant metabolites recovered in feces calculated as amount recovered (Fr_feces) will be calculated as follows:

$$Fr_{feces} = (Ar_f / Dose_{IV}) \times 100$$

9.6 Criteria for Handling Below the Limit of Quantification or Missing Concentrations for Pharmacokinetic Analysis

Plasma and whole blood concentrations below the limit of quantification will be reported as BLQ in the concentration and parameters tables. All BLQ values will be considered as 0.00 for pharmacokinetic and descriptive statistical analyses.

All concentration data-points with time deviations outside the permitted ranges (see Table in section 7.2.1.1 and 7.2.1.2 of study protocol) will be excluded from the descriptive statistics on plasma, whole blood and urine concentrations, explained by a footnote in the appropriate tables and figures, but kept in PK parameters estimation unless very large deviations not allowing for a proper calculation of PK parameters are found: these cases will be discussed during the Data Review Meeting and decision will be fully documented in the DRR.

General rules to handle missing PK data are detailed below, but a case by case evaluation will be performed during the DRM in order to properly handle every specific situation (e.g., missing values at time points close to expected t_{max}). Decisions will be fully documented in the DRR.

Rules on how to deal with missing values when deriving PK AUC:

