- If intermediate values (not the pre-dose, and not more than 3 consecutive) are missing, they will be considered as missing for the PK analysis and automatically imputed by linear interpolation by Phoenix WNL software.
- If multiple (>1) adjacent values are missing or more than 3 values are missing, then the AUCs will be reported, flagged in the result tables and excluded from the statistical analyses. However, such situations will be discussed case by case at the discretion of the clinical pharmacologist (CP) during the review of the data and fully documented in the DRR.
- If the predose value is missing, then the predose value should be set to “0” for the estimation of the PK parameters. In case of missing predose sample, the Phoenix WNL software will automatically use the value of 0 for the estimation of the PK parameters;
- For an estimation of the urine and stool PK parameters, missing predose value do not affect the final parameter estimates because they are not used in the calculation of A_e .

The following rules apply with special situations defined below:

- If an entire concentration-time profile is BLQ, it will be excluded from PK analysis.
- Where 2 or more consecutive concentrations are BLQ at the end of a profile, the profile will be deemed to have terminated and any further quantifiable concentrations will be set to missing for the calculation of the PK parameters, unless they are considered to be a true characteristic of the profile of the drug.
- If a predose plasma and whole blood concentration is missing, it will be set to 0 by default within Phoenix WNL.

Urine and feces concentrations that are missing or BLQ will be set to zero for the calculation of A_{eu} t_{1-t2} and A_{ef} t_{1-t2} .

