9.8 Presentation of Pharmacokinetic Data

For plasma whole blood and urine concentration data, the following rules will apply:

- Values that are BLQ will be set to 0 for the calculation of summary statistics. In listings BLQ values will be reported as “<LLQ” where LLQ will be replaced with the value for the lower limit of quantification
- Arithmetic mean or median values that are BLQ will be presented as 0.

- If any BLQ results (treated as 0) are in a series of summarized data, geometric mean and CV% of geometric mean will be reported as not calculated (NC).

For PK parameters the following rule will apply:

- Geometric mean and coefficient of variation will not be calculated for t_{last} and t_{max} .

Concentration (mass equivalent in mL or mass in mL)/time curves for plasma total [^{14}C], [^{14}C]-CHF6001 and non-radiolabelled CHF6001 will be presented in linear/linear and log/linear scale. Plots will be presented based on arithmetic means and by subject i.e. all individual plasma concentration/time curves will be presented in one graph.

Arithmetic means (+ SD) showing [^{14}C]-total recovery (Fe_f, Fe_u, Fe_tot in the same graph) and ^{14}C -CHF6001 recovery (Fe_f, Fe_u, Fe_tot in the same graph) over the time will be presented using line charts.

All individual concentration data (mass equivalent per mL or mass per mL) and PK parameters will be listed.

In addition, a listing of the actual sampling times relative to drug inhalation will be provided. Concentrations will be summarized by scheduled sampling time by using n, arithmetic mean, SD, CV, median, minimum and maximum.

For each applicable listing, appropriate flag will be added in case of a concentration reported as ND (i.e., not done) or NS (i.e., no sample) or of value BLQ or for PK parameters not estimated / Not calculated.

10 Safety Analyses

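### Counting BLQ parent as 0.00 turns the time-point ratio of plasma [14C]-CHF6001 to total 14C into an exact 0 where only an upper bound is known, and no rule covers a BLQ total

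*SAP*

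**What the plan says.** The plasma parameter table in SAP 9.1 defines the quantity as the "ratio of plasma concentration of [¹⁴ C]-CHF6001 to plasma concentration of [¹⁴ C]-total". The text after the tables says that it "radioactivity will be listed by time point and summarized". Neither place requires the numerator or the denominator to be quantifiable. Sampling for 14C covers pre-dose and 24 times from 5 minutes to 240 hours after the start of infusion (SAP 2, Table 1 footnotes).

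SAP 9.6 states for plasma and whole blood: "All BLQ values will be considered as 0.00 for pharmacokinetic and descriptive statistical analyses". SAP 9.8 repeats this for concentration tables: "Values that are BLQ will be set to 0 for the calculation of summary statistics".

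Five other provisions come near the point:

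- SAP 9.1 has parameters determined where possible, but does not say when a ratio is not possible.
- SAP 9.6 has BLQ concentrations shown as BLQ in the concentration and parameter tables.
- SAP 9.6 has an end-of-profile rule: "Where 2 or more consecutive concentrations are BLQ at the end of a profile, the profile will be deemed to have terminated". It sets later quantifiable values to missing, not the BLQ values.
- SAP 9.8 replaces the geometric mean and geometric CV by NC when a series contains a BLQ zero. It leaves the arithmetic mean, SD, median, minimum and maximum alone.
- SAP 9.8 adds a flag in listings in case "of value BLQ or for PK parameters not estimated / Not calculated".

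No provision deals with a ratio whose numerator or denominator is BLQ.

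**The concern.** A BLQ parent concentration is censored: it lies somewhere between 0 and the LLOQ. Divided by a measured total, it gives a ratio between 0 and LLOQ/total. Substituting 0 picks the lowest value in that interval every time, so the error cannot cancel across subjects. Parent is a component of total. If the two LLOQs are similar, parent drops out first, and the zeros gather at low-concentration times, usually late in the profile.

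The table would then show a falling parent share even if the true share were constant. It would not show which part of the fall comes from the assay limit. A BLQ total is a different gap: the division is by zero, and the programmer must choose between missing, NC and 0 without instruction. Both values should also be BLQ at pre-dose.

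**Working it through.** **Plan's own figure.** None exists. The documents give no LLOQ for either analyte, no expected parent share in this study and no expected ratio. The check applies the rule directly and then shows a range.

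**Rule applied.** Let P be parent, T total, and R = P/T, on a common mass-equivalent scale.

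| Parent | Total | R under SAP 9.6 | What is known |
|---|---|---|---|
| quantifiable | quantifiable | P/T | P/T |
| BLQ | quantifiable | 0/T = 0 | R < LLOQ of parent / T |
| BLQ | BLQ | 0/0 | nothing |
| quantifiable | BLQ | P/0 | nothing usable |

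With equal LLOQs, the bound hidden behind a reported 0 is 1/2 = 0.50 when T is 2 times LLOQ, 1/3 = 0.33 at 3 times, 1/5 = 0.20 at 5 times, 1/10 = 0.10 at 10 times and 1/20 = 0.05 at 20 times.

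**Eight-subject illustration (assumed values).** Take totals of 2, 2.5, 3, 3.5, 4, 4.5, 5 and 6 times LLOQ, equal LLOQs and a true share of 0.30 in everyone. Parent is 0.30 × T, so the first three values (0.60, 0.75, 0.90) are BLQ. The reported ratios are three zeros and five values of 0.30. The mean is 5 × 0.30 / 8 = 0.1875 against a true 0.30; the median is still 0.30.

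**Range by simulation.** Assumptions: total is lognormal with CV 40% and geometric mean k times its LLOQ; the first three scenarios use a lognormal parent share with median 0.30 and CV 20%, so its true mean is 0.30 × √1.04 = 0.306; R is 0 when parent is BLQ; samples with total BLQ are left out; 400,000 draws.

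For the fourth scenario the share comes from Protocol 6.2.1, which puts the two main metabolites in COPD patients about 20-fold and 50-fold below parent. Counting only those two, the share is 1/(1 + 1/20 + 1/50) = 1/1.07 = 0.935.

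| Scenario | True mean | k = 5 | k = 4 | k = 3 | k = 2 |
|---|---|---|---|---|---|
| Share about 0.31, equal LLOQs | 0.306 | 0.26 | 0.21 | 0.13 | 0.04 |
| Same share, parent LLOQ 0.5 × total LLOQ | 0.306 | 0.305 | 0.301 | 0.284 | 0.220 |
| Same share, parent LLOQ 0.3 × total LLOQ | 0.306 | 0.306 | 0.306 | 0.305 | 0.299 |
| Share 0.935, equal LLOQs | 0.935 | 0.935 | 0.935 | 0.934 | 0.919 |

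In the first row parent is BLQ in about 18%, 34%, 60% and 88% of samples, and the median is 0 at k = 3 and k = 2. At k = 10 the bias vanishes. In the last row at most 1.7% of parent values are BLQ.

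**Effect of averaging only the calculable ratios.** In the first scenario the mean becomes 0.314, 0.321, 0.333 and 0.354 at k = 5, 4, 3 and 2, against 0.306. The sign of the bias reverses, because samples with a higher parent share are more likely to be quantifiable. At k = 5 and 4 the error is much smaller than under the zero rule: 0.314 − 0.306 = 0.008 and 0.321 − 0.306 = 0.015, against 0.306 − 0.26 ≈ 0.05 and 0.306 − 0.21 ≈ 0.10.

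**The case against.** The strongest reply is that little depends on this ratio. It is not among the PK variables in Protocol section 8 or SAP 4.1, and no decision rule uses it. Metabolites are characterized by chromatographic profiling with a 10% threshold and by Fr_plasma, an AUC ratio. The plan also reports parent/total ratios for Cmax and AUC(0-∞). The Cmax ratio is not affected in this way, and AUC(0-∞) runs to the last quantifiable concentration plus extrapolation, so it takes in no trailing zeros. All of this stands and limits the consequence.

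Second, the size is unknown. A share near 0.31 has no source in the documents, and the one relevant figure, in Protocol 6.2.1, points to a higher share. It is only an indication: it comes from patients and counts two metabolites. This also stands, which is why a range is given.

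Third, the listings show the LLQ and flag BLQ values, and the parameter tables may show BLQ. A careful reader could trace a zero in a listing to the assay. That helps with individual values, but it does not keep the zero out of a summary mean or median. The where-possible wording does not help either, since 0/T can be computed.

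A reader might go further and infer that the plan will make late circulating radioactivity look like all metabolite, or that the metabolite objective is compromised. The documents do not support this. A 0/0 is undefined rather than zero and says nothing about metabolites; only the case with parent alone BLQ pulls the ratio down. Whether that happens often, or more often with time, depends on LLOQs and concentrations that are not given.

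**Conclusion.** The point holds as a gap in a stated rule. Applied as written, SAP 9.6 gives a parent/total ratio of exactly 0 whenever parent is BLQ and total is quantifiable, and that zero enters the arithmetic mean and median. The direction is certain: the reported parent share can only be biased downward. When total is BLQ the ratio is undefined and the plan is silent.

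The size is conditional. For total between 5 and 2 times its LLOQ, the plausible results run from a reported mean of 0.26 to 0.04 against 0.31 (equal LLOQs), through 0.31 to 0.22 (parent LLOQ half the total LLOQ), to almost no bias (parent LLOQ 0.3 times the total LLOQ, or a share of about 0.93). Each rests on assumed LLOQs, an assumed share and a 40% CV in total.

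The damage is confined to one supplementary descriptive table and its listing. F_inh, mass balance and the Cmax ratio are not affected in this way.

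**What to change.** In SAP 9.1 and 9.6, exempt the time-point ratio from the rule that BLQ counts as 0:

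- Calculate the ratio only where both parent and total are quantifiable; report NC otherwise, including pre-dose.
- Where parent is BLQ and total is quantifiable, list the upper bound, < LLOQ/total, with the parent LLOQ in the numerator.
- In the summary, show at each time point the number of calculable ratios and the number with parent BLQ.
- Optionally, set a cut-off below which no mean is shown, for example when fewer than half of the ratios are calculable. The exact cut-off is a matter of choice.

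The cost is a few sentences in the SAP and one programming condition; no sample or assay changes. There are two downsides. Fewer late time points will carry a summary. The mean of the calculable ratios is also modestly biased upward where some parent values are BLQ (0.314 to 0.321 against 0.306 at 5 and 4 times LLOQ in the equal-LLOQ scenario, more at lower concentrations). The displayed counts make that selection visible, so they are a necessary part of the change.
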